9.3. Variables

The NHWS includes self-reported data on demographics, health characteristics, disease history, and health outcomes. The Table 1 below provides further details on the specific variables that will be assessed in the study.

Table 1. Study Variables

Variable	Role	Operational Definition
Rimegepant vs. triptan use	Exposure	Current Rimegepant users (for sensitivity analysis restricted to acute Rimegepant users with <12 days use per month) vs. triptan users (no OTC, oral route only).
Outcomes: Migraine treatment use and treatment satisfaction		
Migraine medication type (drug or OTC)	Outcome	Defined as drug only, OTC only and both drug and OTC, based on current use of migraine medication classes
Migraine treatment type (acute or prevention)	Outcome	Defined as acute only, prevention only and both acute and prevention, based on current use of migraine medication classes
Total number of acute migraine agent drug (continuous)	Outcome	Total number of acute agent classes (both drug and OTC) used
Total number of acute migraine agent drug (categorical)	Outcome	Including 1 drug class, 2 or more drug classes, and 3 or more drug classes based on the total number of acute agent (both drug and OTC) classes used
Total number of prevention migraine agent drug (continuous)	Outcome	Total number of prevention agent classes (only drug) used
Total number of prevention migraine agent drug (categorical)	Outcome	Including 1 drug class, 2 or more drug classes, and 3 or more drug classes based on the total number prevention agent classes (only drug) used
Current migraine treatments (drugs)	Outcome	Defined as yes or no for current migraine treatments on drug classes including: Rimegepant, triptans, NSAIDs, opioids, barbiturates, ergots, gepants (acute, including Rimegepant), ditans, combination analgesics, other acute drugs, anticonvulsants, beta-blocker, antidepressant, CGRP mAb, botox, and gepant (prevention, including Rimegepant)
Treatment satisfaction (drugs)	Outcome	Treatment satisfaction of drug classes of: Rimegepant, all acute agents, triptans, NSAIDs, opioids, barbiturates, ergots, gepants (acute), ditans, combination analgesics, other acute treatment, all prevention agents,

		anticonvulsants, beta-blockers, antidepressants, CGRPs mAb, botox, and gepant (prevention) Categorized into 7 categories: extremely dissatisfied, very dissatisfied, somewhat dissatisfied, neither dissatisfied nor satisfied, somewhat satisfied, very satisfied, extremely satisfied

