Current migraine treatments (OTC)	Outcome	Defined as yes or no for current migraine treatments on OTC classes of analgesics (acetaminophen only), analgesics (combinations), NSAIDs, other OTCs
Treatment satisfaction-analgesics (acetaminophen only)	Outcome	Treatment satisfaction of OTC classes of analgesics (acetaminophen only), analgesics (combinations), NSAIDs, and other OTCs Categorized into 7 categories: extremely dissatisfied, very dissatisfied, somewhat dissatisfied, neither dissatisfied nor satisfied, somewhat satisfied, very satisfied, extremely satisfied
Outcomes: HRQoL		
RAND-36	Outcome	PCS, MCS, and GCS index scores of the RAND-36 ¹²
EQ-5D-5L	Outcome	Health state utilities and the EuroQoL Visual Analog Scale (EQ-VAS) ¹³
WPAI-GH	Outcome	Absenteeism (% of work time missed because of one's health in the past 7 days), presenteeism (% impairment experienced while at work in the past 7 days because of one's health), overall work impairment (combination of absenteeism and presenteeism), and activity impairment (% impairment in daily activities because of one's health in the past 7 days) among total population, employed, unemployed, and disabled ¹⁴
MIDAS	Outcome	Total score, categorical (grade I-IV), and item scores (1-7) of MIDAS ¹⁵
Outcomes: HCRU		
ER visits	Outcome	Visited ER in past 6 months (yes or no); number of ER visits in past 6 months among total population and participants with ER visits
Hospitalizations	Outcome	Was hospitalized in past 6 months (yes or no); number of hospitalizations in past 6 months among total population and participants with hospitalizations
General practitioner/family practitioner visits	Outcome	Visited general practitioner/family practitioner in past 6 months (yes or no); number of general practitioner/family practitioner visits in past 6 months among total population and participants with general practitioner/family practitioner visits
Cardiologist visits	Outcome	Visited cardiologist in past 6 months (yes or no); number of cardiologist visits in past 6 months among total population and participants with cardiologist visits
Neurologist visits	Outcome	Visited neurologist in past 6 months (yes or no); number of neurologist visits in past 6 months among total population and participants with neurologist visits

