Traditional healthcare provider visits	Outcome	Visited traditional healthcare provider in past 6 months (yes or no); number of traditional healthcare provider visits in past 6 months among total population and participants with traditional healthcare provider visits
Covariates adjusted through IPTW		
Age (continuous)	Potential confounder	Age of participants in years

Sex	Potential confounder	Male vs. female
Race	Potential confounder	Categorized as black, white, and other
Hispanic/Latino	Potential confounder	Yes vs. no
Marital status	Potential confounder	Single/ not living with partner vs. married/ living with partner
Health insurance	Potential confounder	Categorized as private insurance, public insurance, no insurance, and unsure
University education	Potential confounder	Less than university education vs. university education or higher
Annual household income	Potential confounder	Categorized as below median income (<50,000), median income (\$50,000-\$74,999), above median income (\geq \$75,000), and decline to answer
Employed	Potential confounder	Yes (full-time/ part-time/ self-employed) vs. no
Charlson comorbidity index	Potential confounder	Charlson comorbidity index scores with and without patients of score 0 and categories based on scores: 0, 1, 2, 3, and 4+
Body mass index	Potential confounder	Body mass index in kg/m ²
Alcohol use	Potential confounder	Currently drink alcohol vs. currently do not drink alcohol
Smoking status	Potential confounder	Categorized as current smoker, former smoker, and never smoked
Exercise	Potential confounder	Number of days exercise per months
Contraindications	Potential confounder	Ever experienced each of contraindications (angina, arrhythmia, atrial fibrillation, congestive heart failure, heart attack, left ventricular hypertrophy, mini-stroke/transient ischemia attack, peripheral arterial disease /poor circulation, Peripheral vascular disease, stroke, and unstable angina/chest pains)
Cardiovascular risk factors	Potential confounder	Ever experienced each of cardiovascular risks (high blood pressure, high cholesterol, current smoker, type 2 Diabetes, and obesity)
Any contraindications	Potential confounder	Ever experienced any contraindications listed above
Any cardiovascular risk factors	Potential confounder	Ever experienced any cardiovascular risks factors listed above

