Any contraindications or cardiovascular risk factors	Potential confounder	Ever experienced any contraindications or cardiovascular risks factors listed above
Time since migraine diagnosis	Potential confounder	Time since migraine diagnosis in years
Monthly migraine days (continuous)	Potential confounder	Number of days experienced migraine in past 30 days
Monthly headache days (continuous)	Potential confounder	Number of days experienced headache in the past 30 days
Medication overuse (migraine only)	Potential confounder	Yes or no, for migraine-specific medications only
Other covariates that will be evaluated for balance between exposure groups		
Age (categorical)*	Potential confounder	Categorized based on age of participants in years: 18-29, 30-39, 40-49, 50-59, 60-69, 70-79, 80-89
Monthly migraine days (categorical)*	Potential confounder	Categorized based on number of days experienced migraine in past 30 days: <4, 4-9, 10-14, and \geq 15
Monthly headache days (categorical)*	Potential confounder	Categorized based on number of days experienced headache in past 30 days: <4, 4-9, 10-14, and \geq 15
Experience migraines related to menstrual cycle	Potential confounder	Yes vs. no, female participants only

*Categorical age, monthly migraine days, and monthly headache days will be included in inverse probability of treatment weighting (IPTW) adjustment if their distributions are not balanced (standardized mean difference >0.1) after IPTW.

Abbreviations: OTC: over the counter; NSAID: non-steroidal anti-inflammatory drugs; CGRPs mAb: calcitonin gene-related peptide antibodies monoclonal antibodies; HRQoL: health related quality of life; PCS: physical composite score; MCS: mental composite score; GCS: global composite score; WPAI-GH: the Work Productivity and Activity Impairment – General Health; MIDAS: Migraine Disability Assessment Scale; HCRU: health care resource utilization; ER: emergency room; IPTW: inverse probability of treatment weighting

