9.9. Limitations of the Research Methods

The data from the NHWS are self-reported; thus, independent, or clinical verification of responses will not be possible. Due to the self-reported nature of the data, recall error or other response biases may potentially introduce measurement error. However, many of the measures included in the study were developed solely for the purposes of patient self-report (RAND-36, EQ-5D-5L, WPAI-GH, MIDAS), and self-report is a valid and appropriate methodology for assessing subjective outcomes. Because of the cross-sectional nature of the data, causal inferences cannot be drawn, and longitudinal fluctuations in the relationships between study variables cannot be determined. While IPTW will be used to control for potential confounders, it is possible there are other variables that could not be included in the analyses that may at least partially explain any relationships observed in the current study. Finally, while the NHWS is designed to reflect the demographic composition of the general adult population in each country in which it is fielded, it is possible that the data may not be representative of the specific patient subpopulations examined in this study.

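### The weighting and balance lists hold no mental-health history, although MCS, GCS, EQ-5D-5L and WPAI fall under the primary aim, so any difference the listed covariates do not absorb stays unadjusted and unseen

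*Combined protocol and SAP*

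**What the plan says.** Section 8 puts quality of life and work productivity in the primary aim. Table 1 in Section 9.3 makes them concrete as "PCS, MCS, and GCS index scores of the RAND-36", EQ-5D-5L utility and EQ-VAS, and the WPAI-GH scores.

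The part of Table 1 adjusted through IPTW covers:
- demographic, socioeconomic and lifestyle items;
- the Charlson index, given as "Charlson comorbidity index scores with and without patients of score 0" and in five categories from 0 to 4 or more;
- 11 contraindications, beginning "Ever experienced each of contraindications (angina, arrhythmia, atrial fibrillation, congestive heart failure, heart attack, left ventricular hypertrophy", all cardiac, cerebrovascular or peripheral vascular;
- five risk factors, "Ever experienced each of cardiovascular risks (high blood pressure, high cholesterol, current smoker, type 2 Diabetes, and obesity", and three composite flags;
- time since diagnosis, migraine days, headache days and medication overuse.

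A second block, "Other covariates that will be evaluated for balance between exposure groups", adds categorical age, migraine days and headache days, and menstrual migraine. Neither block has a mental-health item. Antidepressants appear in Table 1 only as a migraine drug class, in the role of an outcome.

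On the data source, Section 9.3 says: "The NHWS includes self-reported data on demographics, health characteristics, disease history, and health outcomes". On residual confounding, Section 9.9 says "it is possible there are other variables that could not be included in the analyses". It does not mention mental health.

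**The concern.** A history of depression or anxiety plausibly lowers a mental composite score directly, and plausibly affects the global composite, EQ-5D-5L and WPAI as well. If the two user groups differ on it, part of the difference in these outcomes would not belong to the drug.

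Section 7 gives a reason to expect unlike groups. It describes rimegepant results in patients with insufficient response to triptans, and impaired quality of life and work productivity in triptan users who respond insufficiently. Section 9.2.2 then excludes people who use both drugs. The rimegepant group may therefore contain more patients for whom triptans failed, and these may differ in ways that vascular flags do not capture. Section 7 says nothing about mental health itself, so this is a reason to check and not evidence of a difference.

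Section 8 says the findings may inform communications with payers, so an unseen bias in the quality-of-life outcomes would matter.

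**Working it through.** **Does any part of the plan catch the gap?** Section 9.7 has three layers, followed by two sensitivity analyses.
1. The propensity model contains only the prespecified list.
2. Standardized mean differences (SMDs) are computed for the listed covariates.
3. Regression adjustment is added only for covariates found unbalanced at step 2.
4. The acute-use analysis repeats the same weighting in a smaller rimegepant cohort. The sampling-weight analysis multiplies the same type of propensity weight by the survey weight.

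An unlisted variable is never weighted, checked or regressed, and both sensitivity analyses inherit the omission.

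**The plan's own figures (Section 9.5).** By the normal approximation, n per group = 2(1.96 + 0.8416)²/d². This gives 129 at d = 0.35 and 99 at d = 0.4. The noncentral t gives 129.1 and 99.1, so the stated 130 and 100 reproduce, with power 0.803 and 0.804. The concern changes neither figure.

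**Precision at the actual sizes (Table 2).** SE = √(1/144 + 1/1340) = 0.0877 SD, before any loss from weighting. The effect detectable with 80% power is 2.80 × 0.0877 = 0.246 SD.

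**Illustrative bias.** Bias (SD) = residual prevalence difference × effect of the history on the outcome (SD). Both inputs are assumptions: 5, 10 or 15 points, and 0.5 to 1.0 SD. With no true effect, the probability of p < 0.05 is Φ(−1.96 + b/SE) + Φ(−1.96 − b/SE). For b = 0.10, b/SE = 1.140 and the probability is 0.207. The last column halves the bias, as if the listed covariates had absorbed half the difference.

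| Prevalence difference | Bias, none absorbed | False significance, none absorbed | False significance, half absorbed |
|---|---|---|---|
| 5 points | 0.025–0.050 SD | 5.9–8.8% | 5.2–5.9% |
| 10 points | 0.050–0.100 SD | 8.8–20.7% | 5.9–8.8% |
| 15 points | 0.075–0.150 SD | 13.7–40.2% | 7.1–13.7% |

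Against the detectable 0.246 SD, a bias of 0.025 to 0.15 SD is about 10% to 60%.

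**Allowing for weighting.** If weighting cut the effective triptan sample to a half or a third (assumed), the SE would be 0.092 or 0.096 SD and the top figure would fall from 40.2% to 37.2% or 34.7%. The change is modest because the 144 rimegepant users dominate the SE. With the 112 acute users, unweighted, the SE is 0.098 SD and the range is 5.7% to 33.2%.

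**Would the plan's own rule flag such differences?** The SD of a binary variable is at most 0.5. A 5-point difference therefore gives an SMD of at least 0.05/0.5 = 0.10, and a 10-point difference at least 0.20. So 10 and 15 points lie above the plan's 0.10 threshold at any prevalence, and 5 points lies at or above it. The rule would work if the variable were in the table.

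**The case against.** The strongest objection is that every step from omission to bias comes from outside the documents. They do not say that the 2023 survey records depression or anxiety, that the groups differ on either, or how far either shifts these outcomes. This stands. It limits the claim about size, but not the observation that the variable is absent and unchecked.

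A reader might infer that a mental-health difference passes undiminished into the result. The documents do not support that. Employment, income, exercise, alcohol, smoking, migraine and headache days and medication overuse are all weighted on and may carry part of it. Only the remainder matters.

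A reader might also infer that the vascular items are wasted. They are not: cardiologist visits, hospitalizations, ER visits and the physical composite are outcomes too, and vascular disease plausibly affects them. Nor is the flag for any contraindication or risk factor strictly redundant. With component flags A and B it equals A + B − AB, so it carries their interaction.

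Section 9.9 does concede unmeasured confounding and disclaims causal inference. That helps only in part. The concession is generic and concerns variables that could not be included, while Section 9.7 targets an average treatment effect in the treated.

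Finally, a diagnosis could follow the start of treatment. This is a fair caution, but the ever-experienced items already in the list carry the same uncertainty about timing.

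**Conclusion.** The point holds in a limited form. The plan neither adjusts for nor checks mental-health history, while MCS, GCS, EQ-5D-5L and WPAI are primary-aim outcomes. MCS is the most directly exposed; EQ-5D-5L is exposed as a general health measure.

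The size and direction of any bias are unknown, and it could hide a real difference as easily as create a false one. The range of 0.025 to 0.15 SD, with false significance of about 6% to 40% (about 5% to 14% if half is absorbed), illustrates assumed inputs and does not estimate what will happen.

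Two further assumptions are needed. One is that the Charlson index, whose components the protocol does not list, does not serve as a mental-health measure. The other is that the survey's disease history includes these diagnoses. Without the second, the omission cannot be called a choice of list. The change is worth making because it is cheap, but confidence that it would alter the results is low.

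**What to change.** If the survey's disease history records them, add self-reported ever-diagnosed depression and anxiety to the IPTW-adjusted covariates in Table 1 and to the SMD balance table, for the main analysis and both sensitivity analyses. Do not weight on current symptom scores, which treatment may have changed. Drop the current-smoker flag as a separate term, because the three-level smoking status already contains it. Keep the composite flags.

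If these diagnoses are not recorded, name the gap in Section 9.9 and report a quantitative bias analysis, for example an E-value, for MCS, GCS and EQ-5D-5L.

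The cost is two rows in Table 1 and two terms in the propensity model, with no new data collection. The downside is that a diagnosis made after the drug was started could partly reflect treatment. Using ever-diagnosed history limits this but does not remove it, and the report should say so.

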9.4. Data Sources

This study will use self-reported data sourced from the NHWS. The NHWS is an annual, cross-sectional, internet-based survey of adults conducted across several countries annually. The current study will use data from the 2023 US (N=75,007) NHWS.

9.5. Study Size

Sample size estimates, based upon preliminary feasibility, are provided below, in Table 2. The sample size for this study is fixed by the number of patients in the NHWS database who meet the imposed criteria.

Table 2. Estimated Sample Sizes

Patient Cohorts	n
Overall NHWS sample	75,007
Diagnosed with migraine	8,439
Triptan users (oral route only, no OTC) without Rimegepant use	1,340
Rimegepant users without triptan use	144
Rimegepant users (acute only) without triptan use*	112

*For sensitivity analysis.

Abbreviations: NHWS: National Health and Wellness Survey; OTC: over the counter

A sample size of 1) 130 and 2) 100 in each group (1:1 allocation) will have 80% power to detect an effect size of at least 1) 0.35 standard deviation (SD) units (indicative of at least a “small-to-medium” effect) and 2) 0.4 SD units (indicative of a medium effect), respectively, using a 2-group t-test with a 5% 2-sided significance level. We will have a sample size much greater than 130 in one of our groups, resulting in higher statistical power compared to the 1:1 allocation mentioned above. A total sample size of 100 will have 80% power to detect an effect size from a chi-square distribution of at least 0.33 (indicative of at least a “small-to-medium” effect) using a chi-square test with a 5% 2-sided significance level and 3 degrees of freedom. There will be sufficient power to detect a “small-to-medium” effect of Rimegepant user vs. triptan use on the outcomes in the main analysis, and sufficient power to detect a medium effect in the sensitivity analysis with acute Rimegepant users only.

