9.2.2. Exclusion Criteria

Patients meeting the following criteria will not be included in the study:

1. Currently on both Rimegepant and triptan use at time of survey.

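### The unlimited power claim in Section 9.5 holds for full-cohort outcomes before weighting, but not for continuous outcomes in subsets with fewer than about 72 Rimegepant users, nor for one-arm or 7-category satisfaction

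*Combined protocol and SAP*

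**What the plan says.** Section 9.5 makes two power statements and one conclusion.

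- **Continuous outcomes:** the planning sizes are 130 per group (main analysis) and 100 per group (sensitivity analysis), at 1:1 and 80% power. The main target is "an effect size of at least 1) 0.35 standard deviation (SD) units"; the sensitivity target is 0.40 SD, called medium. Both calculations are made "using a 2-group t-test with a 5% 2-sided significance level".
- **Categorical outcomes:** "A total sample size of 100 will have 80% power to detect an effect size from a chi-square distribution of at least 0.33", at 5% with 3 degrees of freedom.
- **Conclusion:** sufficient power for a small-to-medium "effect of Rimegepant user vs. triptan use on the outcomes in the main analysis", and for a medium effect in the acute-only sensitivity analysis.

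Table 2 expects 144 Rimegepant users (112 acute-only) and 1,340 triptan users.

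Table 1 (Section 9.3) lists several outcomes that only part of a cohort can contribute to:

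- Six visit or stay counts have a version restricted to people who had that visit or stay, for example "number of ER visits in past 6 months among total population and participants with ER visits".
- WPAI-GH is reported overall and separately for employed, unemployed and disabled respondents.
- Satisfaction is recorded by drug or OTC class, on seven levels.

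Section 9.2.2 excludes anyone "Currently on both Rimegepant and triptan use at time of survey". Section 9.7 sends categorical variables to chi-square or Fisher tests and continuous ones to t-tests.

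**The concern.** The closing sentence extends a calculation based on 130 or 100 per group to every outcome in Table 1, including those that a minority of the 144 Rimegepant users may contribute to. No subset size or subset power is given anywhere. The sample is fixed by the database, so the power paragraph mainly guides how results are read. Section 8 says that the findings may support discussions with payers. A non-significant difference in, say, the number of ER visits among ER users could then be taken as adequately powered evidence of little difference, on the strength of a statement that may not cover that comparison.

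**Working it through.** **Method.** For a two-group t-test with sizes n1 and n2, difference d in SD units and two-sided alpha 0.05: λ = d / √(1/n1 + 1/n2), df = n1 + n2 − 2, and power = P(noncentral t with df, λ exceeds the 97.5% point of central t). For the chi-square test, noncentrality = N·w², compared with the 95% point of chi-square on the stated df.

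**Step 1: reproduce Section 9.5.**
- 130 per group, d = 0.35: λ = 0.35/√(2/130) = 2.82; power 80.3%.
- 100 per group, d = 0.40: λ = 0.40/√(2/100) = 2.83; power 80.4%.
- Chi-square, N = 100, w = 0.33, 3 df: noncentrality 100 × 0.33² = 10.89; power 79.9%.

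All three agree with the plan.

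**Step 2: full cohorts (Table 2), before weighting.**
- 144 vs 1,340, d = 0.35: λ = 3.99; power 97.9%; detectable difference at 80% power 0.246 SD.
- 112 vs 1,340, d = 0.40: λ = 4.07; power 98.2%; detectable difference 0.276 SD.

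**Step 3: smallest adequate subset.** Assume the same share of each cohort is in the subset, so that the ratio stays at 1,340 to 144 (or 112).
- d = 0.35: 71 Rimegepant users give 79.9% and 72 give 80.5%, so 72 are needed (72/144 = 50%). Against all 1,340 triptan users the minimum would be 68.
- d = 0.40, acute-only: 53 give 79.8% and 54 give 80.5%, so 54 are needed (54/112 = 48%).

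**Step 4: range over assumed shares.** The documents give no shares; these are illustrations, before weighting.

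| Share in subset | Main cohort, n | Power at 0.35 SD | Detectable (SD) | Acute-only, n | Power at 0.40 SD | Detectable (SD) |
|---|---|---|---|---|---|---|
| 10% | 14 vs 134 | 24% | 0.78 | 11 vs 134 | 25% | 0.88 |
| 20% | 29 vs 268 | 43% | 0.55 | 22 vs 268 | 44% | 0.62 |
| 30% | 43 vs 402 | 59% | 0.45 | 34 vs 402 | 60% | 0.50 |
| 40% | 58 vs 536 | 71% | 0.39 | 45 vs 536 | 73% | 0.44 |
| 50% | 72 vs 670 | 80.5% | 0.35 | 56 vs 670 | 82% | 0.39 |
| 60% | 86 vs 804 | 87% | 0.32 | 67 vs 804 | 88% | 0.36 |

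(Powers use the unrounded sizes, such as 14.4.)

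**Step 5: employment strata.** Three mutually exclusive strata would need 3 × 72 = 216 Rimegepant users; there are 144. Even at the more lenient 68, the total is 204. At most two strata can reach 72, and then only with 72 in each and nobody in the third. If disabled respondents are instead counted within the unemployed, all three reach 72 only if the split is exactly even and every unemployed respondent is disabled.

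**Step 6: satisfaction.**
- With users of both drugs excluded, nobody in the Rimegepant cohort rates triptans and nobody in the triptan cohort rates Rimegepant. Each of those rows has one empty arm.
- Seven levels in two groups give (7 − 1)(2 − 1) = 6 df. At N = 100 and w = 0.33, power is 69%; the effect detectable with 80% power is w = 0.37.

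**Step 7: weighting.** Section 9.5 makes no allowance for it. If weighting cut the effective triptan size to 268 (an assumption), power at 0.35 SD would be 92% in the full cohort, 74% in a 60% subset and 66% in a 50% subset.

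**The case against.** The best defence is that nothing in Section 9.5 is miscalculated. It plans on 130 and 100 per group, below the available 144 and 112, and ignores most of the 1,340 triptan users, so there is slack: the claim survives until about half the Rimegepant cohort is lost. That stands.

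Each visit or stay count also has a total-population version and a yes/no version, so the restricted counts are additions to outcomes with full-cohort size. RAND-36, EQ-5D-5L and MIDAS are not restricted by definition either. That also stands, and it rules out the broader reading that the study's principal comparisons lack power.

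A reader might also infer that every subset outcome is underpowered. The documents do not support this. With no shares given, general practitioner visitors, the employed or users of any acute agent could each exceed half the cohort.

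Nor do the SD thresholds apply to class satisfaction, which is categorical. Under the plan's own chi-square terms, a 10% subset (N about 148) still has 87% power at w = 0.33 with 6 df, though a 5% subset (N about 74) has only 54%. At this allocation (144/1,484 = 9.7% Rimegepant users), w = 0.33 also represents a larger between-arm difference than at 1:1. The 3 df is not wrong in itself: it fits a four-level outcome such as MIDAS grade. It does not fit seven levels.

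The empty arms are strictly a question of estimability, and those rows can be reported descriptively. But Section 9.5 excepts no outcome, and Section 9.7 plans to compare the cohorts on satisfaction.

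Finally, Section 9.7 foresees small samples, naming resource use and an example of fewer than 30. This chooses a test; it does not qualify the power claim. With 29 Rimegepant users, power at 0.35 SD is 46% even against all 1,340 triptan users.

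**Conclusion.** The concern holds as a limit on the scope of the claim; the stated power figures themselves are correct.

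- **Sound before weighting:** t-test outcomes in the full cohorts (97.9% at 0.35 SD; 98.2% at 0.40 SD for acute-only).
- **Not delivered, on the documents alone:** the three WPAI-GH employment strata cannot all reach about 72 Rimegepant users, barring the degenerate overlap in Step 5; satisfaction with Rimegepant and with triptans has no between-cohort comparison; and the 3-df statement does not describe 7-level satisfaction (69%, not 80%, at N = 100 and w = 0.33).
- **Undetermined:** which restricted visit counts fall short. Any with fewer than about 72 Rimegepant users (54 acute-only) does, assuming equal shares in both cohorts. Under assumed shares of 10% to 40%, power at 0.35 SD runs from 24% to 71%.

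The consequence lies in interpretation. No equivalence claim is planned, and neither the sample nor the estimand would change. Correcting the statement is still worthwhile, because it is the only guide the plan gives for reading null results.

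**What to change.** In Section 9.5:

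1. Limit the 0.35 and 0.40 SD claims to outcomes measured in the full cohorts, and say that they are before weighting.
2. Add, from the existing survey, the number of Rimegepant and triptan users with each visit or stay type and in each employment stratum, with the detectable difference for each.
3. Recompute the chi-square statement with 6 df for satisfaction, keeping 3 df only for four-level outcomes.
4. Label as descriptive the one-arm satisfaction rows and the continuous subset outcomes with fewer than about 72 Rimegepant users (about 54 acute-only), and state that null results there are not adequately powered for these effects.

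The cost is one reworded paragraph and a few counts from data already collected. The downside is that the stated power becomes less favourable for some outcomes.
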